9.4.3 ANALYSIS OF THE SECONDARY ENDPOINT(S)

- Our secondary outcomes of interest are self-compassion scale (continuous), FAAM (continuous), PROMIS (continuous).
- Normally distributed data will be evaluated with ANOVA. Nonparametric data will be evaluated with the Mann-Whitney U.
- Subjects will be excluded from analysis if they are missing secondary outcomes of interest.

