3 OBJECTIVES AND ENDPOINTS

OBJECTIVES	ENDPOINTS	JUSTIFICATION FOR ENDPOINTS
Primary		
To assess rates of return to dance without limitations after start of non-operative treatment in dancers recovering from foot and ankle injuries	Return to dance after treatment of injury	Investigators want to see the immediate effect of the mental health app on short-term recovery and return to dance, but also the longer lasting effects (if present) after injury recovery.
Secondary		
To assess self-compassion in the recovering dancer during and after the nonoperative treatment of their foot and ankle injury To assess musculoskeletal function during and after the recovery process	FAAM, PROMIS, and Self Compassion scores collected at 3, 6, 12, 18, and 24 months	Investigators want to see the immediate effect of the mental health app on short-term recovery and return to dance, but also the longer lasting effects (if present) after injury recovery.
Tertiary/Exploratory		
None		

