6 STUDY INTERVENTION

6.1 STUDY INTERVENTION(S) ADMINISTRATION

6.1.1 STUDY INTERVENTION DESCRIPTION

The study intervention will be mental health exercises via the SuperBetter app for dancers participating in PT rehab for foot or ankle injuries. The control will be PT rehab only, without implementation of the SuperBetter app.

Subjects who enroll and are randomized into the treatment arm will be assisted in clinic to log into the app SuperBetter. They will be added to the group run by the “host”/study staff. The SuperBetter app offers a daily exercise on a schedule that will be managed by the “host” or study staff. Subject will complete 1 full activity per day. This activity will not exceed 15 minutes in total including app boot-up, but the full activity itself will not exceed 10. These activities ask participants to practice different exercises that might be found in Cognitive Behavioral Therapy, such as mindfulness. They are framed like a game for engagement, where the subject can “get a power up” when they take 30 seconds to breathe deeply and think of 3 loved ones, as an example. 1 full daily activity is constituted by 4 to 6 very brief activities similar to the previously described.

Both groups will undergo physical exams at their normally scheduled orthopedic appointments at baseline, 8 weeks, 3 months, 6 months, 12 months, 18 months, and 24 months where presence/absence of reinjury, return to dance, adherence to PT and/or the SuperBetter app, type(s) of dance, and hours of dance per week will be assessed. Both groups will be asked to complete the PROMIS, SCS, and FAAM at baseline, 3-, 6-, 12-, 18-, and 24 months.

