8 STUDY ASSESSMENTS AND PROCEDURES

8.1 EFFICACY ASSESSMENTS

- **Physical examination (all visits)**
 - Presence/absence of reinjury
 - Return to Dance status
 - Adherence to PT and/or SuperBetter app exercises
 - Type of dance
 - Hours of dance per week
- **Administration of questionnaires (all visits)**
 - PROMIS + PROMIS mental health
 - SCS
 - FAAM

The **Self Compassion Scale (SCS)** is a validated measure of self-compassion in individuals, which is a concept or trait associated with psychological wellbeing including, potentially, lower depression and anxiety (7). It asks patients questions about their self-kindness or, conversely, self-judgment during everyday times of difficulty. We will be using the short form version which has been shown to be an economical alternative to the long Self Compassion Scale, saving time for subjects by reducing the length of the questionnaire by half, while still being reliable (16). This survey will take approximately 5 minutes to complete.

The **Foot and Ankle Ability Measure (FAAM)** is a validated measure of physical function for a broad range of musculoskeletal conditions of the lower leg, foot, and ankle (17). It asks patients questions about their current level of difficulty performing different everyday tasks, activities, and sports motions. This survey will take no more than 10 minutes to complete.

The **Patient-Reported Outcomes Measurement Information System (PROMIS)** is an effective measure seen to be useful in evaluating pain interference in diverse settings, and mental health among musculoskeletal patients (19,20). It asks questions regarding patients' pain interference with activity and daily living, mobility, and current depression and anxiety symptoms. This survey will take no more than 10 minutes to complete.

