9 STATISTICAL CONSIDERATIONS

9.1 STATISTICAL HYPOTHESES

- Primary Efficacy Endpoint(s):
 - Null Hypothesis (H_0): There will be no difference in self compassion scores to return to unrestricted dance at 3 months between the mental health app group and control group.
 - Alternative Hypothesis (H_1): Self compassion and return to unrestricted dance is expected to be improved in the mental health app treatment group compared to control group.
 - Type of Comparison: Superiority
 - Time Point: 12 months
 - Analysis Method: Logistic regression or Fisher's exact test depending on data distribution.
- Secondary Efficacy Endpoint(s):
 - Change in Self-Compassion Scale scores over time (repeated measures ANOVA or nonparametric equivalent) in experimental group compared to control group
 - Association of self-compassion with FAAM and PROMIS scores (correlation/regression)
 - Time to initial return to dance (Kaplan-Meier with log-rank test or Cox regression)
 - Reinjury incidence (descriptive comparison by self-compassion group)

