9.4 STATISTICAL ANALYSES

9.4.1 GENERAL APPROACH

- Descriptive statistics will be presented. Continuous data will be evaluated with the Shapiro-Wilk test of normality, data that is considered normal with that test will be evaluated with Levene's test of homogeneity of variances. Data that are found to be parameteric with both tests, will be treated as normally distributed and evaluated with analysis of variance (ANOVA). Continuous data that fails either test of normality listed above will be evaluated with the Mann-Whitney U. Continuous data will be presented as means \pm standard deviation, with the range. Non-parameteric continuous data will include the median as well.
- Categorical data will be evaluated with Pearson's Chi-square, or Fisher's exact test. Odds ratios will be calculated for categorical data that is found to be significantly different among the two groups.
- Statistical significance will be defined as $p < 0.05$.

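### For SCS, section 9.1 plans repeated-measures ANOVA of change over time, but 9.4.3 routes data to ANOVA or Mann-Whitney U with no visit or summary named

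*Protocol*

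**What the plan says.** Protocol section 9.1 lists as its first secondary efficacy endpoint "Change in Self-Compassion Scale scores over time (repeated measures ANOVA or nonparametric equivalent"), experimental against control. For FAAM and PROMIS, 9.1 lists only their association with self-compassion.

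Section 9.4.3 takes SCS, FAAM and PROMIS together as continuous outcomes: "Normally distributed data will be evaluated with ANOVA. Nonparametric data will be evaluated with the Mann-Whitney U". It adds: "Subjects will be excluded from analysis if they are missing secondary outcomes of interest". The route to one test or the other is set in 9.4.1, by Shapiro-Wilk and then Levene: "Continuous data that fails either test of normality listed above will be evaluated with the Mann-Whitney U".

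On timing, the table in section 3 has "FAAM, PROMIS, and Self Compassion scores collected at 3, 6, 12, 18, and 24 months", and section 6.1.1 adds a baseline measurement: "Both groups will be asked to complete the PROMIS, SCS, and FAAM at baseline". Section 9.4.3 mentions no visit, no change score and no baseline term.

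**The concern.** SCS measures what the trial sets out to improve. Two sections of one document prescribe its analysis and they do not agree. A joint analysis of change over five follow-up visits and a rank test on one number per person answer different questions. An SAP could add detail to either, but it could not follow both. The trial is unblinded (section 6.3), so an analysis left open until the data are seen is harder to defend.

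Two further features of 9.4.3 affect all three scales. Baseline scores are collected, but no use of them is stated, and in a trial of about 50 they can add useful precision. Participants with missing scores are to be excluded, while section 8.2 tells participants that they may skip any question.

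**Working it through.** **The text, side by side (SCS)**

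- *Quantity.* 9.1: change over time. 9.4.3: the scale as a continuous outcome, with no statement of score or change.
- *Visits.* 9.1: implied to be joint across visits. 9.4.3: none named; section 3 lists five follow-ups as collection times.
- *Parametric branch.* 9.1: repeated-measures ANOVA. 9.4.3: ANOVA, which can be read as the same thing.
- *Nonparametric branch.* 9.1: an equivalent of repeated-measures ANOVA. 9.4.3: Mann-Whitney U. This test compares two independent samples with one value per person. It cannot jointly analyse five correlated visits. It could match 9.1 only if applied to a single summary, such as change at one visit.

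The firm conflict is therefore on the nonparametric branch, together with the undefined quantity and visit.

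**Size of the supporting points**

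The protocol gives no effect size, SD or power for these scales, so there is no stated figure to reproduce. Inputs: 50 planned participants (section 9.2), assumed split 25 and 25; two-sided 0.05; 80% power. The baseline to follow-up correlation r and the missing fraction m are assumptions.

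*Baseline.* The noncentral t distribution gives a detectable difference of 0.809 SD for a follow-up-only comparison. Adjusting for baseline multiplies this by √(1 − r²). A change score multiplies it by √(2(1 − r)), with equal SDs at both times.

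| Assumed r | Follow-up only | Change score | Baseline-adjusted |
|---|---|---|---|
| 0.3 | 0.81 | 0.809 × √1.4 = 0.96 | 0.809 × √0.91 = 0.77 |
| 0.5 | 0.81 | 0.809 × √1.0 = 0.81 | 0.809 × √0.75 = 0.70 |
| 0.7 | 0.81 | 0.809 × √0.6 = 0.63 | 0.809 × √0.51 = 0.58 |

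Allowing for estimation of the slope changes the last column only slightly, to 0.78, 0.71 and 0.58.

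*Exclusion, applied visit by visit.*
- m = 5%: 50 × 0.95 = 47.5, so about 47 (24 + 23); detectable difference 0.84 SD.
- m = 10%: 50 × 0.90 = 45 (23 + 22); 0.86 SD.

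*Exclusion of anyone missing any of the five follow-ups, with independent missingness.*
- m = 5%: 50 × 0.95⁵ = 38.7, so about 39 (20 + 19); 0.92 SD.
- m = 10%: 50 × 0.90⁵ = 29.5, so about 30 (15 + 15); 1.06 SD.

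*Pre-test.* This was simulated at one visit with normal scores, equal variances, 25 per arm and 20,000 runs, with Shapiro-Wilk applied to pooled scores or per arm. Type I error was 5.1% (pooled) and 5.0% (per arm), the same as ANOVA alone. Power at 0.809 SD was 79.3% and 79.5%, against 79.7% and 79.9% for ANOVA alone.

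**The case against.** The best defence is that 9.4.3 is a general statement and 9.1 its specific form for SCS. Section 9.4.3 says only ANOVA, and repeated-measures ANOVA is an ANOVA. A reader might infer that 9.4.3 prescribes a two-group ANOVA and so contradicts 9.1 on that branch too. The document does not say so: the explicit two-group wording is in 9.4.5, on baseline characteristics. This part of the defence stands, but it does not rescue the Mann-Whitney branch.

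A reader might also infer that 9.4.3 rules out the baseline score. It is silent. A change score contains the baseline, and 9.1 speaks of change. Leaving baseline out would not bias a randomised comparison; it costs precision. The follow-up-only figure of 0.81 SD is therefore only one possible starting point.

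It is tempting to argue that choosing the test by pre-test damages the error rates. With normal data it has almost no effect, so it is not a main argument.

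Nor does the exclusion rule necessarily remove many participants. Per visit the loss is small, and whether a skipped item makes a whole score missing depends on scoring rules that the protocol does not give.

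Finally, covariance structure and similar detail may be left to an SAP. That is fair, but the conflict between two stated methods and the stated exclusion rule are not omissions.

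**Conclusion.** The point holds for SCS. Sections 9.1 and 9.4.3 can lead to different analyses, because Mann-Whitney U is not the counterpart of a joint repeated-measures analysis and 9.4.3 fixes neither visit nor summary. This rests on the text alone and on no assumed number. It does not extend to FAAM and PROMIS, for which 9.1 states no comparison between arms.

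The supporting points apply to all three scales and are smaller. The gain from baseline adjustment ranges from slight to substantial, depending on the assumed correlation and on whether the alternative is a follow-up score or a change score. The exclusion rule matters materially only if a participant missing any visit is dropped entirely, which the protocol does not state.

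The sponsor should correct this before data are seen. It affects secondary endpoints, not the primary one.

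**What to change.** State one analysis in both 9.1 and 9.4.3: a likelihood-based linear mixed model for each score, namely SCS, FAAM and each PROMIS domain collected (section 8.1 describes "pain interference with activity and daily living, mobility, and current depression and anxiety symptoms"). Take baseline and all five follow-ups as responses, with a baseline mean common to both arms, visit effects, and arm-by-visit effects at follow-up. This adjusts for baseline and keeps participants with partial data. Pre-state the covariance structure and a simpler fallback, since about 50 participants may not support an unstructured six-by-six matrix.

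Name one main visit contrast per score in advance and treat the other visits as supportive. The visit is the sponsor's choice. Section 9.1 does not settle it: under the primary endpoint its null hypothesis reads "no difference in self compassion scores to return to unrestricted dance at 3 months", while the time point given there is 12 months.

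Delete the pre-test rule and the exclusion rule for these endpoints. Mann-Whitney U on change at the named visit may stay as a sensitivity analysis. Copying 9.1 into 9.4.3 would end the contradiction, but classical repeated-measures ANOVA also drops incomplete cases.

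The cost is revised wording and modest extra programming, with no new data. The downside is reliance on model assumptions with about 50 participants.

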9.4.4 SAFETY ANALYSES

This is not applicable to this study.

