2 INTRODUCTION

2.1 STUDY RATIONALE

A dance injury can create psychological distress (11). We aim to explore the effect on return to dance, recurrence of injury and mental health during and after treatment of dance injury via the use of a mental health intervention. Low self-compassion specifically has been linked to psychological distress in athletes which can impair the recovery process during injury (21). This is an unexplored area in the dance population, which we aim to examine through this study. The gamified mental health app SuperBetter has been shown to have a positive and comparable effect on anxiety and depression scores when compared with group Cognitive Behavioral Therapy (CBT) interventions (5). We do not currently have the resources to administer group CBT interventions and therefore are using the gamified app as a proxy. It has also been shown to be an effective intervention with improved outcomes in treatment of adolescent concussion patients (1). Its use has not been explored in adolescent athletes. Thus, this project aims to enhance self-compassion in adolescent dancers recovering from a non-operative foot

and ankle injury by using a gamification mental health app to augment the physical therapy and home exercise program during the recovery course.

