8.3.4 TIME PERIOD AND FREQUENCY FOR EVENT ASSESSMENT AND FOLLOW-UP

The occurrence of an adverse event (AE) or serious adverse event (SAE) may come to the attention of study personnel during study visits and interviews of a study participant presenting for medical care, or upon review by a study monitor.

All AEs including local and systemic reactions not meeting the criteria for SAEs will be captured on the appropriate case report form (CRF). Information to be collected includes event description, time of onset, clinician's assessment of severity, relationship to study product (assessed only by those with the training and authority to make a diagnosis), and time of resolution/stabilization of the event. All AEs occurring while on study must be documented appropriately regardless of relationship. All AEs will be followed to adequate resolution.

Any medical condition that is present at the time that the participant is screened will be considered as baseline and not reported as an AE. However, if the study participant's condition deteriorates at any time during the study, it will be recorded as an AE.

Changes in the severity of an AE will be documented to allow an assessment of the duration of the event at each level of severity to be performed. AEs characterized as intermittent require documentation of onset and duration of each episode.

The Principal Investigator will record all reportable events with start dates occurring any time after informed consent is obtained until 7 (for non-serious AEs) or 30 days (for SAEs) after the last day of study participation. Events will be followed for outcome information until resolution or stabilization.

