9.3 POPULATIONS FOR ANALYSES

- Intent-to-Treat (ITT): All participants who initiate treatment
- Per-Protocol (PP): Participants with full follow-up data and $\geq 80\%$ adherence to recovery protocol
- Safety Population: All participants (reporting adverse events and reinjury)
- Exploratory Subgroups: Participants may be stratified into tertiles or above/below median self-compassion for exploratory comparisons

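### No comparison of adverse events or reinjury by randomised arm is specified: Section 9.4.4 rules out safety analyses, and the one analysis naming reinjury is grouped by self-compassion

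*Protocol*

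**What the plan says.** The protocol collects the relevant data in both arms. Section 8.1 lists "Presence/absence of reinjury" among the items assessed at all visits, and Section 6.1.1 applies this to both groups from baseline to 24 months. Section 8.3.4 states: "All AEs occurring while on study must be documented appropriately regardless of relationship".

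Section 9.3 then defines "Safety Population: All participants (reporting adverse events and reinjury", so a population exists for these outcomes. Section 9.4.4, the place for the matching analysis, reads in full: "This is not applicable to this study".

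Reinjury has one named analysis, in the secondary list of Section 9.1: "Reinjury incidence (descriptive comparison by self-compassion group". In the same list, the change in Self-Compassion Scale (SCS) score is analysed "in experimental group compared to control group". Section 9.4.3 leaves reinjury out: "Our secondary outcomes of interest are self-compassion scale (continuous), FAAM (continuous), PROMIS (continuous". The objectives and endpoints table in Section 3 does not mention it either.

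The rationale in Section 2.1 does: "We aim to explore the effect on return to dance, recurrence of injury and mental health during and after treatment of dance injury".

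**The concern.** Two separate faults meet here.

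The first is a contradiction. A population is defined for reporting adverse events and reinjury, the data are required, and the analysis is then declared inapplicable. A statistical analysis plan written to this protocol would inherit that exclusion.

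The second is the grouping for reinjury. An effect of the app is a contrast between randomised arms. A contrast between participants with higher and lower self-compassion is observational. If the split uses scores taken after randomisation, treatment itself may shift who falls in which group.

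At stake is a report that gives a by-arm result on return to dance, the primary endpoint, with no specified by-arm result on reinjury. A reader would reasonably ask whether more or earlier return to dance came with more reinjury. The same applies to emotional distress from the app, which Sections 2.3.1 and 8.3.5 name as a possible harm. Only the app arm is exposed to the app, so arm is the grouping that could show an excess.

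**Working it through.** The plan states no adverse event rate, reinjury rate or power for either outcome, so there is no figure to reproduce. The check is mainly of the text.

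**1. Adverse events.** Section 8.3.4 requires collection, Section 9.3 supplies a population, and Section 9.4.4 rules the analysis out. No other section names an analysis of adverse events.

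**2. Reinjury.** Sections 6.1.1 and 8.1 collect it, Section 9.3 includes it in the safety population, and Section 2.1 names it as an aim. Section 9.1 analyses it by self-compassion; Sections 3 and 9.4.3 omit it.

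**3. What the self-compassion grouping means.** Section 9.3 describes exploratory strata as tertiles or a median split of self-compassion. The SCS item in Section 9.1 names the two arms explicitly, which suggests the authors wrote arm where they meant arm. Sections 9.4.7 and 9.4.9 plan no subgroup or exploratory analyses, so the split has little support elsewhere.

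**4. What such a split can show.** The protocol does not say which visit's score defines the groups.
- Baseline score: randomisation balances the groups across arms apart from chance, so the contrast carries no information on the app's effect.
- Later score: Sections 1.1 and 2.1 state that the app is intended to raise self-compassion, so membership may be a consequence of treatment. The contrast mixes any arm effect with whatever else separates dancers with high and low scores.

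Neither version answers the aim in Section 2.1.

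**5. What a by-arm table could deliver.** Section 9.2 plans 50 participants, or 50 / 2 = 25 per arm if allocation is equal (an assumption, suggested by the 19 per group in the same section). With zero events in n participants, the exact two-sided 95% upper bound is 1 − 0.025^(1/n):
- n = 25: 1 − 0.025^(1/25) = 0.137, or 13.7%.
- n = 19: 1 − 0.025^(1/19) = 0.176, or 17.6%.

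Power of a two-sided 0.05 Fisher's exact test at 25 per arm, for assumed reinjury rates (the documents give none):

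| Control | App | Power |
|---|---|---|
| 20% | 10% | 0.09 |
| 30% | 15% | 0.15 |
| 40% | 20% | 0.23 |
| 10% | 30% | 0.31 |

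The comparison would therefore be descriptive. It could not exclude a sizeable difference.

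**The case against.** **The general rule may already cover it.** Section 9.4.1 sends categorical data to a chi-square or Fisher's exact test and refers to differences between the two groups. Reinjury is recorded as present or absent in both groups, so the rule could be stretched to reach it. This stands to the extent that one cannot say the arms will never be compared, which a reader might infer from Section 9.4.4 alone. But the general rule names neither adverse events nor reinjury, and the specific statements in Sections 9.1 and 9.4.4 point the other way.

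**The grouping may be a slip of wording.** Section 9.2 speaks of experimental and control groups and, in the same sentence, of a median split. The protocol thus blurs arm with self-compassion stratum, and the reinjury line may simply mean the arms. This cannot be excluded. It changes the diagnosis from a poor choice to an ambiguous label; the line needs correcting either way.

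**The dilution cannot be quantified from the documents.** A reader might try. With equal arms, 70% of app and 30% of control participants in the high group, and reinjury depending on arm alone, the high-minus-low difference is (0.7 − 0.3) × the arm difference, so 20 points would appear as 8. With a 50/50 split it would be zero. Both are assumed scenarios. Section 9.2 argues that self-compassion itself influences recovery; if it also affects reinjury directly, the group difference could exceed the arm difference or take the opposite sign.

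**The study is low risk.** Section 8.3.6 calls it minimal risk and Section 8.3.3.3 expects no adverse events. Nor do the documents say that earlier return to dance raises reinjury; that is a reviewer's question. These points limit the weight of the finding but do not remove the contradiction or the stated aim.

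**Conclusion.** The point holds in this form: no section specifies a comparison of adverse events or reinjury by randomised arm. Section 9.4.4 contradicts Sections 9.3 and 8.3.4, and the one analysis naming reinjury, as worded, cannot show the app's effect on recurrence of injury. This is more than detail deferred to a statistical analysis plan, because the protocol states an exclusion and names a grouping.

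The conclusion on grouping rests on reading the Section 9.1 phrase with Section 9.3, as a split on the SCS score. On the alternative reading, as a label for the arms, the defect is one of terminology.

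The effect on the plan's figures is nil, and the bias from the self-compassion grouping cannot be sized from the documents. The by-arm result would be modest in precision: upper bounds of 13.7% (25 participants) or 17.6% (19) even with no events, assuming all are observed. It should be corrected, but it does not threaten the primary analysis.

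**What to change.** - **Section 9.4.4:** replace the statement with text such as: Adverse events, serious adverse events and reinjury will be tabulated by randomised arm in all randomised participants. Counts and percentages will be given, with a risk difference and 95% confidence interval for reinjury. These summaries are descriptive, and no powered test is planned.
- **Section 9.1:** change the grouping for reinjury from self-compassion to randomised arm. Keep any self-compassion split as descriptive only, and state which visit's score defines it.
- **Section 9.4.3:** make it agree with Section 9.1 on whether reinjury is a secondary outcome. Section 3 should follow the same decision.

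The cost is one table from data already collected and a few lines of protocol wording. No extra participants, visits or assessments are needed.
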